# 8.5 Reporting and Follow-Up of Pregnancies

### 8.5.1 Period of Collection and Follow-up

In case of pregnancies detected between the time of signature of the ICF and enrollment of the subject, the subject will be considered as a screening failure. In that situation, the pregnancy will not be reported to the Sponsor, however, the identified pregnancy(ies) must be captured in the screening failure CRF. No pregnancy form will be filled.

In case of pregnancies detected between enrollment and prior to randomization, subject will be discontinued, and reported as "enrolled but not randomized" subject. Early termination procedures shall apply. No pregnancy form will be filled.

Any pregnancy detected after randomization must be reported by the Investigator within 24 hours. This also includes pregnancies spontaneously reported to the Investigator after the end of the study for a subject.

Any pregnancy that was potentially associated with exposure to IP (*IQOS* or cigarette) will be followed-up until an outcome is reached (e.g., normal delivery, spontaneous abortion, or voluntary termination) and also until 8 weeks after delivery.

Any pregnancy complication, adverse pregnancy outcome or maternal complications will be recorded as an AE accordingly.

# 8.5.2 Reporting of Pregnancies

A dedicated pregnancy form will be used to report pregnancy cases.

The procedure to report a pregnancy and provide any additional/follow-up information to UBC Pharmacovigilance and Sponsor is the same and performed within the same timelines as the one described for an SAE (Section 8.3).

The Investigator is responsible for informing the corresponding IEC of any pregnancy case that was reported during the study, as determined by local regulations.

# 8.6 Adverse Events Leading to Discontinuation

Subjects who are discontinued from the study because of an AE will undergo the early termination procedures (Section 9.6), as soon as practical after discontinuation, and will enter the 28-day safety follow-up period. In general, AEs will be followed-up until resolved,

### **Confidentiality Statement**

Philip Morris Products SA	Clinical Study Protocol	Confidential
P1-EXC-01-EU	Version 3.0 / 2 May 2019	Page 80 of 151

stabilized (i.e., no worsening of the event), or a plausible explanation has been found and until the end of the study. Any AEs or SAEs that are ongoing at the end of the safety follow-up period will be managed as described in Section 8.2.6.

# 8.7 Investigational Product Malfunction and Misuse

Any occurrences of device events, including *IQOS* malfunction (e.g., holder does not charge when inserted into the charger) or misuse by a subject (use not in accordance with its label and instructions), will be documented by the Investigator or his/her designee using a device issue log.

Investigational product misuse may result in use-related hazards (Section 2.3.4).

Furthermore, any misuse or malfunction of *IQOS* that leads to an AE/SAE will follow the same processes as described above for the reporting of the AE/SAE.

# 9 STUDY ACTIVITIES

The procedure can be performed at any time during the visit, unless otherwise specified. Assessments will be conducted only by qualified and trained site personnel.

# 9.1 Screening

The screening visit can be performed on more than one day but has to be completed (including safety laboratory results) within 28 days prior to V2. The sequence of assessments/events before VO2max test is given for illustrative purposes. The VO2max test should only be performed after all clinical assessment have been performed and the subject is judged healthy without any contraindication to perform exercise testing as per the Investigator's judgement. If the inclusion and exclusion criteria are satisfactorily met, the site staff will contact the subject to arrange his/her next visit (V2) to the site.

Table 5 shows the procedures that will be performed at V1:

Time	Blood Sample	Procedures	Additional Information
Start of Procedure		V1	
		Informed consent for study participation	Including section on optional participation in sub-study interviews
		Informed consent for biobanking	Optional
After ICF signature		Information on the risk of smoking, smoking cessation advice and debriefing on IQOS	
		Demographic data collected (sex, date of birth/age, and race)	
		Medical history/concomitant disease	
		Prior medication (within 4 weeks prior to V1) and concomitant medication	

# Table 5Time Schedule – V1

### **Confidentiality Statement**

Philip Morris Products SA	Clinical Study Protocol	Confidential
P1-EXC-01-EU	Version 3.0 / 2 May 2019	Page 82 of 151

Time	Blood Sample	Procedures	Additional Information
Start of Procedure		V1	
		Questionnaire on tobacco and nicotine containing product use history and habits to assess smoking history	
		IPAQ-short	
		Vital signs (blood pressure, pulse rate, respiratory rate)	After resting for at least 5 minutes in supine position
		Collection of spot urine for:	
		
 
Urinalysis safety panel
 
Urine drug screen
 
Urine cotinine test
 
	
	I	Urine pregnancy test	
		Clinical laboratory parameters (hematology, clinical chemistry)	
	$\checkmark$	Serology (HIV, hepatitis B and C)	
		Physical examination	
		Height, weight, calculation of BMI	
		IQOS demonstration	Without product use
		mHealth wearable demonstration	
		Alcohol breath test	
		CO breath test	
		Spirometry	Has to be done at least 1 hour after smoking After resting in sitting position for at least 15 minutes prior to testing.
		ECG	After resting for at least 10 minutes in supine position prior to recording.

### **Confidentiality Statement**

Philip Morris Products SA	Clinical Study Protocol	Confidential
P1-EXC-01-EU	Version 3.0 / 2 May 2019	Page 83 of 151

Time	Blood Sample	Procedures	Additional Information
Start of Procedure		V1	
After having performed all clinical		VO₂max test	Exercise testing should be performed at least 30 min after spirometry assessments.
assessments			VO 2 max and the work produced will be recorded.
			After completing the test water will be provided ad libitum .
		AE/SAE recording	At any time during the day.
			If the V1 is performed on two separate days, the AE/SAE questions will be asked again
		Readiness to comply with study procedures	
		Inclusion/exclusion criteria check	

Abbreviations:

AE = Adverse event; BMI = Body mass index; CO = Carbon monoxide; ECG = Electrocardiogram; HIV = Human immunodeficiency virus; IPAQ= International Physical Activity Questionnaire; SAE = Serious adverse event.

# 9.2 Enrollment and Familiarization with Exercise Test

Visit 2 (V2) will be scheduled 7±1 days prior to V3 (randomization).

Table 6 shows the procedures that will be performed at V2.

### **Confidentiality Statement**

Philip Morris Products SA	Clinical Study Protocol	Confidential
P1-EXC-01-EU	Version 3.0 / 2 May 2019	Page 84 of 151

Time	Blood Sample	Procedures	Additional Information
Start of Procedure		V2	
Prior to enrollment		Collection of spot urine for: • Urine cotinine test • Urine drug screen • Urine pregnancy test Confirmation of smoking status by CO breath test. Alcohol breath test	Confirmation of eligibility. Has to be done in the morning prior to enrollment
		Enrollment	
After enrollment		Vital signs (blood pressure, pulse rate, respiratory rate)	After resting for at least 5 minutes in supine position
		Information on the risk of smoking, smoking cessation advice	
		Exercise capacity test – bike ergometer	Work to complete will be based on the highest wattage level reached during VO 2 max test during V1. After completing the test water will be provided ad libitum .
		mHealth wearable kit distribution and training on how to wear, handle and charge the device	
		Product use diary distribution	
		Concomitant medication	
		AE/SAE recording	At any time during the day.
Abbreviations.			

Abbreviations:

AE = Adverse event; CO = Carbon monoxide; SAE = Serious adverse event.

During the  $7\pm1$  days between V2 and V3, subjects having signed the optional section of the ICF will have an interview (by phone or computer) on the topic of health and functioning lasting around 60 minutes.

# 9.3 Baseline and Randomization

Table 7 shows the procedures that will be performed at V3. All baseline assessments should be performed before randomization.

Time	Blood Sample	Procedures	Additional Information
Start of Procedure		V3	
		Urine pregnancy test	
Before breakfast/ snack	$\checkmark$	Clinical laboratory parameters (hematology, clinical chemistry and urinalysis)	At least 8 hours of fasting Hematocrit and Hemoglobin results will also be used to calculate blood volume
	$\checkmark$	Biological health markers	At least 8 hours of fasting
	$\checkmark$	Biobank blood collection	Only if optional ICF signed At least 8 hours of fasting
		Breakfast/Snack	
		Biobank saliva and sweat collection	Only if optional ICF signed
		FTND questionnaire	
		Lifestyle questionnaire	
		RPC scale	
		Vital signs (blood pressure, pulse rate, respiratory rate)	After resting for at least 5 minutes in supine position
		ECG	After resting for at least 10 minutes in supine position prior to recording.
		Physical examination	
		Weight, body fat percentage and waist circumference	
		Cough assessment questionnaire (VAS scale, and 3 Likert scales)	
		CO breath test	

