## 7.5.9 Determination of Blood Composition and Volume

Hemoglobin mass ( $Hb_{mass}$ ) will be quantified using an automated system (e.g. OpCO, Detalo Instruments, Denmark or similar). First, a venous blood sample will be drawn to measure hemoglobin, hematocrit and COHb, after which the CO re-breathing procedure will be performed. Using the system a precise volume of CO is inhaled and re-breathed by the subject

Data and information contained in this document are considered to constitute trade secrets and confidential commercial information, and the legal protections provided to such trade secrets and confidential information are hereby claimed under the provisions of applicable law. No part of this document may be publicly disclosed without the written consent of Philip Morris Products S.A

Philip Morris Products SA	Clinical Study Protocol	Confidential
P1-EXC-01-EU	Version 3.0 / 2 May 2019	Page 63 of 151

for 10 min. During the re-breathing period 100% O2 is administered to the subject on a demand basis, and due to the small volume of CO administered and the continuous O2 supplementation arterial O2 is barely affected. After completion of the re-breathing procedure COHb will be measured again. Then based on the resulting increase in COHb, the mass of hemoglobin will be calculated. Red blood cell volume, plasma volume and blood volume will be derived from measures of Hbmass, [Hb] and hematocrit.

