### Table 7 Time Schedule – V3 Baseline

**Confidentiality Statement** 

Philip Morris Products SA

P1-EXC-01-EU

Time	Blood Sample	Procedures	Additional Information
Start of Procedure		V3	
30-60 min before VO₂max test		Smoke a cigarette	Only subjects willing to
After all clinical assessments		VO 2 max test	HR and VO 2 will be recorded at rest and at each 25W increase
During VO₂max test		Borg RPE scale	At rest and at each 25W increase
During VO₂max test	$\checkmark$	Capillary blood lactate sampling to measure lactate levels	At rest and at each 25W increase
Before start of exercise capacity		Snack and water ad libitum	Snack to be consumed at least 30 min before start of exercise capacity test
60±5min after VO₂max test		Exercise capacity test – bike ergometer	Work to complete will be based on the highest wattage level reached during VO 2 max test at V3. After completing the test water will be provided ad libitum .
After exercise capacity test Before CO- rebreathing	$\checkmark$	COHb	Results will be used to assess 1) CO exposure and 2) to calculate blood volume
After exercise capacity test	$\checkmark$	Determination of blood volume by CO-rebreathing	Blood will be sampled after CO- rebreathing for COHb determination
As late as possible during the day/visit		Spot urine collection for urinary exposure markers and biobanking	Collection of urine for biobanking only if optional ICF signed
		Concomitant medication	
		AE/SAE recording	At any time during the day.
Before randomization		Product preference question	As an instruction to answer this question, subjects will be informed that their response will not influence the randomization process.

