### **Confidentiality Statement**

Philip Morris Products SA

P1-EXC-01-EU

Clinical Study Protocol Version 3.0 / 2 May 2019

Page 92 of 151

Time	Blood Sample	Procedures	Additional Information
Start of Procedure		V43	
		Biobank saliva and sweat collection	Only if optional ICF signed
		Vital signs (blood pressure, pulse rate, respiratory rate)	After resting for at least 5 minutes in supine position
		Weight,body fat percentage and waist circumference	
		RPC scale	
		CO breath test	
30-60 min before VO 2 max test		Subjects in IQOS -1 and IQOS -2 arms will use a HeatStick. Subjects in the cigarette arm will smoke a cigarette.	Only subjects willing to.
After all clinical assessments		VO₂max test	HR and VO 2 will be recorded at rest and at each 25W increase
During VO₂max test		Borg RPE scale	At rest and at each 25W increase
During VO₂max test	$\checkmark$	Capillary blood lactate sampling to measure lactate levels	At rest and at each 25W increase
After VO 2 max test		Snack and water ad libitum	Snack to be consumed at least 30 min before start of exercise capacity test
60±5min after VO₂max test		Exercise capacity test – bike ergometer	Work to complete will be based on the highest wattage level reached during VO 2 max test at V3. After completing the test water will be provided ad libitum.
After exercise capacity test Before CO- rebreathing	$\checkmark$	СОНЬ	Results will be used to assess 1) CO exposure and 2) to calculate blood volume
After exercise capacity test	$\checkmark$	Determination of blood volume by CO-rebreathing	Blood will be sampled before CO- rebreathing to for Hematocrit and Hemoglobin and after CO- rebreathing for COHb determination

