# **Confidentiality Statement**

provided to such trade secrets and confidential information are hereby claimed under the provisions of applicable law. No part of this document may be publicly Data and information contained in this document are considered to constitute trade secrets and confidential commercial information, and the legal protections disclosed without the written consent of Philip Morris Products S.A This document is an uncontrolled copy of RD\_SMF02\_049133\_CSP\_P1-EXC-01-EU, 1.0,CURRENT

Philip Morris Products SA Clinical Study Protocol

P1-EXC-01-EU

Version 3.0 / 2 May 2019

Confidential

Page 123 of 151

	Screening	Familiarization	Baseline	Exercise Tests Acute Effect	Training Visits	Medical Visit	Training Visits	Medical Visit	Training Visits	Exercise Tests Training Effect	Discharge / Early Termination	28-day Safety follow-up
Visit	1	2	3	4	5-14	14	15-28	28	29-42	43	44	
Bike ergometer – Exercise capacity 		•	•	•						•		
mHealth wearable demonstration	•											
mHealth wearable distribution and training		•										
mHealth wearable return										•	• - if ET	
Randomization			•									
Demonstration of IQOS	•											
IQOS starter kit distribution and device return			•							•	•- if ET	
Product use diary Distribution/Return		•								•	• - if ET	
Bike ergometer 40-min training session 					•		•		•			
Body fat percentage			•	•						•		
Waist circumference			•	•						•		
Blood composition and volume (CO re-breathing method) including blood sample for hematocrit Hb and COHb before CO-			•							•		

 The time to complete a pre-defined work as fast as possible on a bike ergometer. The criteria for completion of the test is the completion of the pre-defined work (kcal) determined as 1.25 times the highest wattage reached during the VO2max test at V1 for the test at V2, and at V3 for the tests at V3, V4 and V43.

 Training sessions will be performed according to Appendix 2 and will be adjusted according to the subject's resting and maximal heart rate.

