5.2 Blood composition as determined by CO re-breathing method

Blood composition variables as determined by CO re-breathing method will be calculated according to the method proposed in Siebenmann (Siebenmann, et al. 2017). The corresponding endpoints are hemoglobin mass (g), red blood cell volume (mL), plasma volume (mL) and total blood volume (mL).

The change in the fraction of carboxyhemoglobin in blood samples obtained pre- and post-CO rebreathing is calculated in percentages as:

 $\Delta COHb = \% COHbPost - \% COHbPre.$

Confidentiality Statement

Philip Morris Products SA.	Statistical Analysis Plan	Confidential
P1-EXC-01-EU	Final 2.0	Page 23 of 71
Related to PMI-RRP-WKI-112487		

The absorbed number of CO molecules is calculated in moles as: nCOabsorbed = Patm * VCOabsorbed/(R * T)where R is the ideal gas constant [0.008206 L*atm/(mol*K)]. The volume of CO that has been absorbed (VCOabsorbed), atmospheric pressure (Patm), and room temperature (T) should be entered in liters, atmospheres, and Kelvin, respectively.

The value of the volume of CO that is absorbed is normalized to 25 C° and 1013 mbar (i.e. 1 atm) and called VCOabsorbed, norm. Thus in the equation above Patm = 1 atm and T = 298.15K. The absorbed number of CO molecules is therefore,

nCOabsorbed = 1* VCOabsorbed,norm / (82.06 *298.15) = VCOabsorbed,norm / 24466.189.

Given that 1 mol of hemoglobin binds 4 mol of CO the tagged number of hemoglobin molecules (nHbtagged) is calculated in moles as:

nHbtagged = nCOabsorbed/4.

The total number of hemoglobin molecules is calculated in moles as: nHbtotal = (nHbtagged/ Δ COHb) * 100.

Based on the molar mass of hemoglobin, the hemoglobin mass (in grams) is calculated as: Hbmass = nHbtotal * 6.44×10^4 g/mol. With the equations above, a VCOabsorbed, norm of 90 mL and a $\triangle COHb$ of 10 % results in 592.25 g HBmass.

Intravascular volumes (in mL) are calculated as: Red blood cell volume, i.e. RBCV = Hbmass * Hct/[Hb] Total blood volume, i.e BV = RBCV/Hct Plasma volume, i.e PV = BV - RBCVHct is entered in these equations as absolute fractions (i.e., not in %), whereas [Hb] is entered in g/mL.

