¹² The VO₂max test will be performed on a bike ergometer using a mouthpiece and nose clip. Measurements will begin with the subjects resting for 3 min seated on the bike ergometer whereafter the workload will be increased by 25W every 60 sec until volitional fatigue. Subjects should keep cadence between 60 and 90 rpm during the test. At V3, V4 and V43, heart rate and VO₂ will be recorded at rest and at each 25W increase.

¹³ The time to complete a pre-defined work as fast as possible on a bike ergometer. The criteria for completion of the test is the completion of the pre-defined work determined as 25% more work than was completed during the VO₂max test at V1 for the test at V2, and at V3 for the tests at V3, V4 and V44.

Confidentiality Statement

L	
⋸	
1.0.CURREN	
5	
\overline{O}	
P1-EXC-01-EU.	
4	
2	
×	
Ϋ	
₽ ₽	
Ś	I
80	
000	
òo	
5	
Ľ	
ົດ	
2	1
of RD	I
ov of RD SMF01 810308 SAP	
cop	-
cop	-
cop	-
rolled cop/	-
rolled cop/	-
rolled cop/	-
an uncontrolled cop/	-
s an uncontrolled cop	-
ent is an uncontrolled copv	-
ent is an uncontrolled copv	-
document is an uncontrolled copv	-
ent is an uncontrolled copv	-

Confidential	ge 62 of 71
Coi	Page

Statistical Analysis Plan

Final 1.0

Related to PMI-RRP-WKI-112487

P1-EXC-01-EU

Philip Morris Products SA.

SAP_P1-EXC-01-EU

	Screen ing	Familiar ization	Base- line	Exercise Tests Acute Effect	Training Visits	Medical Visit	Training Visits	Medical Visit	Training Visits	Exercise Tests Training Effect	Discharge / Early Termination	28-day Safety follow- up
Visit	٢	7	e	4	5-14	14	15-28	28	29-42	43	44	
IQOS starter kit distribution and device return			•							٠	•- if ET	
Product use diary Distribution/Return		•								•	• - if ET	
Bike ergometer 40-min training session ¹⁴					•		•		•			
Body fat percentage			•	•						•		
Waist circumference			•	•						•		
Blood composition and volume (CO re-breathing method) including blood sample for hematocrit Hb and COHb before CO-rebreathing, and COHb after CO-rebreathing.			•							•		
Perceived exertion - RPE Borg scale 15			•							•		
Blood COHb%			•	•		•		•		•		
Capillary blood lactate levels ¹⁶			•							•		

¹⁴ Training sessions will be performed according to Appendix 2 and will be adjusted according to the subject's resting and maximal heart rate.

¹⁵ Rate of perceived exertion will be measured at rest and at every 25 W increase during the VO₂ max test until the end of the test.

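### The protocol contradicts itself on which haemoglobin and haematocrit sample feeds blood volume at V3; if its visit tables are followed, within-arm changes in plasma and total blood volume are confounded by sampling state

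*Protocol*

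**What the plan says.** Five places describe the Hb and Hct sample, and they do not agree.

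- **Protocol Table 7 (V3).** The note on the safety-laboratory row, taken before breakfast after at least 8 hours of fasting, reads "Hematocrit and Hemoglobin results will also be used to calculate blood volume". The rows after the exercise capacity test list COHb only. The re-breathing row says "Blood will be sampled after CO- rebreathing for COHb determination".
- **Protocol Table 11 (V43).** There is no safety-laboratory row; that panel is drawn at V44. The re-breathing row, timed after the exercise capacity test, says "Blood will be sampled before CO- rebreathing to for Hematocrit and Hemoglobin".
- **Protocol section 7.5.9.** The general method makes no distinction by visit: "First, a venous blood sample will be drawn to measure hemoglobin, hematocrit and COHb", followed by re-breathing.
- **Protocol Appendix 1.** The blood-volume row, marked at V3 and V43, specifies "re-breathing method) including blood sample for hematocrit Hb and COHb before CO" re-breathing.
- **SAP section 13.1, schedule of events.** The same row, also marked at V3 and V43, reads "including blood sample for hematocrit Hb and COHb before CO-rebreathing".

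SAP section 5.2 gives the formulas but names no source sample. SAP section 9.6.1.1.4 analyses change from V3 at V43 in Hb mass, red cell volume, plasma volume and total blood volume. Within-arm and between-arm estimates are both reported with 95% confidence intervals.

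**The concern.** Total blood volume is Hb mass divided by Hb concentration, and plasma volume is what remains after subtracting red cell volume. Anything that changes Hb and Hct at one visit only therefore appears as a change in volume.

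A site working from the visit tables would sample at V3 in a rested, fasting subject. At V43 it would sample after a maximal test, about an hour of rest and a timed ride. Protocol section 4.3 offers blood volume before and after the intervention as a measure of exercise capacity that does not depend on motivation. A difference in sampling state between the two visits weakens that before-and-after comparison. The estimates at stake are the within-arm changes in two of the four blood-composition endpoints.

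**Working it through.** **Inputs.** The formulas and the worked Hb mass come from SAP section 5.2. The resting Hb and Hct values, and the proportional shift c between sampling states, are assumptions, because the documents give none.

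**Reproducing the plan's figure.** With 90 mL of CO absorbed and a COHb rise of 10%:

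Hb mass = (90 / 24466.189) / 4 / 10 × 100 × 64400 = 592.246 g, against the SAP's 592.25 g.

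(The gas constant printed earlier in that section, 0.008206, would give 5922 g if used literally with litres. The SAP's working line uses 82.06 with mL, which is correct, so this does not affect the point.)

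**Formulas reduced.**

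- Red cell volume RBCV = Hb mass × Hct / [Hb]
- Total blood volume BV = RBCV / Hct = Hb mass / [Hb]
- Plasma volume PV = BV − RBCV = Hb mass × (1 − Hct) / [Hb]

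**Effect of a shift.** Suppose nothing truly changes, but Hb and Hct at V43 are both multiplied by (1 + c).

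- RBCV: the factor cancels, so there is no change.
- BV: becomes BV / (1 + c), a change of −BV × c / (1 + c).
- PV: changes by the same number of mL as BV. As a fraction of resting PV this is −c / [(1 + c)(1 − Hct)].
- Hb mass: does not use [Hb] or Hct, so there is no change.

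**Numbers, with Hb mass 592.25 g.** Case A assumes Hb 15 g/dL and Hct 0.45 (BV 3948 mL, PV 2172 mL). Case B assumes Hb 13 g/dL and Hct 0.39 (BV 4556 mL, PV 2779 mL).

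| Assumed shift c | BV and PV change, mL (A / B) | BV change | PV change (A / B) |
|---|---|---|---|
| −2% | +81 / +93 | +2.0% | +3.7% / +3.3% |
| +2% | −77 / −89 | −2.0% | −3.6% / −3.2% |
| +5% | −188 / −217 | −4.8% | −8.7% / −7.8% |
| +10% | −359 / −414 | −9.1% | −16.5% / −14.9% |

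Check for case A at +5%: 0.05 / (1.05 × 0.55) = 0.0866, or 8.7%.

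The mL figures scale with Hb mass; the percentages do not. With an assumed Hb mass of 750 g, Hb 15 g/dL and Hct 0.45, PV is 2750 mL and a +5% shift gives 5000 × 0.05 / 1.05 = 238 mL, again 8.7%.

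**If the other three places govern.** Table 7 times the V3 COHb sample before re-breathing but after the capacity test. If Hb and Hct come from that same sample, both visits are post-exercise, and the artefact is zero when the exercise effect on Hb and Hct is equal at the two visits.

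**The case against.** A reader might infer from Tables 7 and 11 that the blood-volume results simply carry an exercise artefact, that it pushes every change downward, and that it hides a training gain. The documents do not support that.

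- **The V3 source is not settled.** Section 7.5.9, Appendix 1 and the SAP schedule all put Hb and Hct in the pre-re-breathing sample. Only the Table 7 note points to the fasting draw, and by saying the results are also used it does not exclude the other sample. What can be shown is a contradiction; the artefact follows only if Table 7 was followed. This stands. The general permission in Protocol section 9 to do procedures at any time does not remove the contradiction, because these rows carry specific timings.
- **The sign is not established.** The V3 draw follows a fast. The V43 draw follows breakfast, a snack and water freely available after each test, and no interval is set between the end of exercise and the draw. Net dilution is possible. This stands, so the range above includes both signs.
- **Between-arm contrasts are largely safe.** All four arms do the same tests under the same tables, so a common shift cancels. Only a part that differs by arm would remain. This stands.
- **The study tests no hypothesis, and these are two endpoints within Objective 4.** True, but the within-arm changes with intervals are planned results and would be read as estimates.
- **Matching on the post-exercise sample is not perfect.** The VO2max test runs to volitional fatigue, so trained subjects may work harder at V43 and the shift may differ between visits. This is a fair limit on that remedy, and the fix below gives an alternative.

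**Conclusion.** The contradiction is certain: the visit tables give different sampling states for V3 and V43, three other places give a common one, and SAP 5.2 does not choose between them.

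The bias is conditional. If the visit tables were followed, within-arm changes in plasma and total blood volume are confounded by sampling state. The direction is downward if net haemoconcentration persists at the V43 draw, and upward if food and fluid cause net dilution. The size rests entirely on the assumed shift: roughly −3% to −17% in plasma volume for +2% to +10%, and +3% to +4% for −2%. These figures also assume that Hb and Hct shift by the same proportion. It would go too far to conclude that the reported changes are biased, or biased against a training gain.

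**What to change.** Reconcile Protocol section 7.5.9, Table 7, Table 11, Appendix 1 and the SAP schedule so that Hb and Hct come from the same sampling state at V3 and V43. There are two workable choices.

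1. **Pre-re-breathing venous sample at both visits.** This is the simplest: three of the five places already say it, and at V3 blood is already drawn there for COHb. The cost is an Hb and Hct reading on that blood, with no extra venepuncture. Any difference in exercise response between visits remains.
2. **Fasting, pre-exercise draw at both visits.** It exists at V3 as the safety-laboratory draw and at V43 as the biological health marker draw. The cost is adding Hb and Hct at V43. This also avoids a difference in exercise response between visits.

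Delete the conflicting note or row, and name the chosen sample in SAP 5.2. If V3 data exist only from the fasting sample, say so in the SAP and flag the within-arm plasma and total blood volume changes as confounded by sampling time. Apart from the reading itself, the cost is wording.
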